7.1 Nonclinical and Clinical Safety Data

The toxicity of elenbecestat has been evaluated in oral repeated-dose toxicology studies of up to 26 weeks duration in rats and 39 weeks in cynomolgus monkeys. Nonclinical findings of note include immunologic-related findings at 30 mg/kg and above in monkeys (including 1 cytomegalovirus-related death at 60 mg/kg). An additional completed monkey immunology study suggested that lymphocytes and lymphocyte subsets may be suitable markers to monitor potential immunotoxicity or immunomodulation by elenbecestat in a clinical setting. An oral fertility and early embryonic development study in male rats has been conducted, in which elenbecestat was administered orally by gavage once a day to male rats for 28 days before, and throughout the mating period, at doses of 30, 100, or 300 mg/kg. There were no effects on mating, fertility, and early embryonic development at any dose level. The NOAEL was 100 mg/kg for male general toxicity and 300 mg/kg for male reproduction in this study. Therefore, there are no contraceptive requirements for male subjects participating in this study. (revised per Amendment 04) Further details of the nonclinical data to date with elenbecestat can be found in the Investigator's Brochure.

The clinical program to date includes 9 Phase 1 studies and 1 Phase 2 study: (revised per Amendment 02)

Study E2609-A001-001 (Study 001) was a randomized, double-blind and placebo-controlled, SAD study that investigated doses ranging from 5 to 800 mg in healthy adult subjects (aged 30 to 55 years) and elderly subjects (50 mg dose only, aged 65 to 85 years).

Study 002 was a randomized, double-blind and placebo-controlled multiple ascending dose (MAD) study in healthy male and female subjects aged 50 to 85 years. CSF was collected before and following the 14 days of dosing to assess the PK levels of elenbecestat and the pharmacodynamic (PD) effects on BACE activity and A β levels.

Study E2609-A001-003 (Study 003) was a single-center, open-label study in healthy subjects investigating the effects of drug-drug interactions by itraconazole, rifampin, and donepezil on the PK properties of elenbecestat. It also investigated the effects of elenbecestat on the PK properties of digoxin. (revised per Amendment 04)

Study E2609-A001-004 (Study 004) was a single-center, randomized, double-blind, placebo-and active-controlled, single dose, 4-treatment crossover study to evaluate the effects of elenbecestat on QTc interval in healthy subjects (thorough QT study). Two dose levels of elenbecestat were evaluated in this study, including a 50 mg therapeutic dose and a 200 mg suprathreshold dose.

Study E2609-A001-005 was an open-label, single-dose study to determine the metabolism and elimination of [14 C]E2609 in healthy male subjects (aged 18 to 55 years).

Study E2609-A001-006 (Study 006) was a randomized, placebo-controlled, single-dose study conducted at a single center to evaluate the safety, tolerability, PK, and PD of elenbecestat in healthy adult male Japanese and white subjects.

Study E2609-A001-007 (Study 007) was a single-center, open-label, randomized, 3-treatment crossover study of single oral doses of a capsule formulation of elenbecestat under fasted conditions and a tablet formulation administered under fed and fasted conditions in healthy subjects to evaluate their relative bioavailability.

Study E2609-A001-101 (Study 101) has been completed. This study was a Phase 1 randomized, double-blind, placebo-controlled, Bayesian adaptive design study in adults aged 50 to 85 years with subjective memory complaints and who qualified as having MCI or mild AD.

For Study E2609-A001-103 (Study 103), PK analysis has been completed and a clinical study report is in preparation. This study was a Phase 1 hepatic impairment special population study that enrolled 8 subjects with mild hepatic impairment (Child-Pugh Class A) and 8 subjects with moderate hepatic impairment (Child-Pugh Class B) and compared them to an equal number of age, sex, and body weight matched healthy control subjects following administration of a single oral 50 mg dose of elenbecestat. (revised per Amendment 02)

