In Study 003, a drug-drug interaction study, PK results showed that itraconazole (a potent inhibitor of cytochrome P450 [CYP] 3A4 and carboxylesterase-2 [CES2]) caused a mild increase (by approximately 70%) of the area under the concentration \times time curve (AUC) of elenbecestat. Rifampin (a potent CYP3A4 inducer) caused a mild decrease (by approximately 20%) of the AUC of elenbecestat. Donepezil (a moderate CES2 inhibitor) caused a mild increase (by approximately 20%) of the AUC of elenbecestat when coadministered with elenbecestat but not when dosed at least 2 hours apart from elenbecestat. Elenbecestat (which inhibits the P-glycoprotein 1 transporter) did not affect the PK properties of digoxin. Nonclinical studies also indicated that other CYP pathways apart from CYP3A4 would not be major pathways of metabolism of elenbecestat. Based on these results, it is not considered necessary to impose restrictions during elenbecestat treatment on the use of concomitant medications that may be CYP3A4 inhibitors or other CYP enzymes inhibitors. Similarly, it was also not considered necessary to restrict the use of concomitant medications that are inducers of CYP450 enzymes. Given the results of study 003 moderate to strong CES2 enzyme inhibitors are not permitted for a period of 5 half-lives or 7 days (whichever is longer) before randomization and until the last treatment visit.

However, simvastatin use is permitted only with once daily evening administration. Simvastatin use is recommended with night time administration as physiological studies showed that most cholesterol is synthesized when dietary intake is at its lowest. It is therefore expected that the PK interaction between elenbecestat and simvastatin is minimized because simvastatin is thought to mainly inhibit CES2 in the intestine when elenbecestat will not be present, as it will be administered in the morning.

Study 004, a thorough QT study, demonstrated that single doses of elenbecestat up to the suprathreshold dose of 200 mg did not have any clinically meaningful impact on the QTcF, heart rate, PR, or QRS intervals. The results from the moxifloxacin arm of the study

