- v: Site staff will contact the subject or the study partner the day before the PK blood sampling to provide instructions that subjects must not take their study drug at home on the day of the PK blood sampling. During this telephone contact with the subject or the study partner, the site staff should document the time that the subject took their study drug that day, ie, the day before the PK blood sampling.
- w: Two plasma PK samples will be obtained: 1 sample at predose (trough) and another sample 1 to 6 hours postdose at Visits 3, 4, 6, 7, 9, and 11 and another sample 4 to 8 hours postdose at Visit 13 (or ED). Therefore, subjects or their study partners must be instructed not to take their study drug at home on the day the PK sampling is performed. Instead, subjects will take the study drug at the clinic after collection of the predose PK sample. At Visit 13 (or ED), the PK blood sample should be collected shortly before or after completing the LP for subjects participating in the CSF substudy. If the study drug is temporarily suspended, postdose PK samples will not be required. If at an ED Visit, the subject has already stopped study drug, then postdose PK samples are not required.
- x: PD and exploratory biomarker blood samples should be collected at fasting or at least 2 hours after the most recent meal and, as far as is feasible, samples should be taken at the same time of day at all visits. Samples should be taken predose at Visits 2, 3, 4, 6, 7, 9, 11, 13 (or ED), 14, and 15. (revised per Amendments 01, 03, and 04)

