9.7.1.6.1 PRIMARY EFFICACY ANALYSIS

The primary analysis will be based on an intent to treat philosophy without regard to adherence to treatment. The primary analysis of the change from baseline in CDR-SB at 24 months will be performed to compare elenbecestat 50 mg per day versus placebo using a linear mixed effects model for repeated measures (MMRM) on the FAS. The MMRM model will include fixed effects of treatment group, visit, treatment group by visit interaction, baseline CDR-SB, baseline CDR-SB by visit interaction, and randomization stratification variables (ie, region [7 levels], clinical dementia [yes, no], and concurrent AD medication use at randomization [Visit 2] [yes, no]). *ApoE4* status may be included in the model if appropriate. (revised per Amendments 01, 02, and 06) An unstructured covariance matrix will be employed to model the covariance of within subject effect; if MMRM fails to converge then a covariance structure with fewer parameters from the following list will be employed according to the prespecified order in the list until the MMRM converges. The list of covariance structure will include Heterogeneous Toeplitz, Toeplitz, Heterogeneous Compound Symmetry, and Compound Symmetry. This primary analysis will include all observed post baseline data of the change from baseline in CDR-SB without imputation of missing values. The treatment effect for elenbecestat versus placebo will be compared at 24 months based on MMRM model. The LS means and difference in LS means between elenbecestat treatment group and placebo, and corresponding 95% CI will be presented.

The null hypothesis is that there is no difference in the mean change from baseline in CDR-SB at 24 months between elenbecestat 50 mg per day and placebo. The corresponding alternative hypothesis is that there is a difference in the mean change from baseline in CDR-SB at 24 months between elenbecestat 50 mg per day and placebo.

The primary analysis will be repeated to minimize the impact of change in concomitant AD medications where efficacy data after initiation of new AD medications and increase of current AD medications will be censored.

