9.7.1.7 Pharmacokinetic, Pharmacodynamic, Pharmacogenomic, and Other Biomarker Analyses

9.7.1.7.1 PHARMACOKINETIC ANALYSES

Safety Analysis sets will be used for individual elenbecestat plasma and CSF concentration listings. The PK Analysis Set will be used for the summaries of elenbecestat plasma and CSF concentrations.

A population PK approach will be used to characterize the PK of elenbecestat. The effect of covariates (ie, demographics) on elenbecestat PK will be evaluated. The PK model will be parameterized for clearance (CL) and volumes of distribution. Derived exposure parameters such as AUC will be calculated from the model using the individual posterior estimate of CL and dosing history.

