9.7.1.7.2 PHARMACOKINETIC-PHARMACODYNAMIC

The PK/PD relationship between CSF biomarker levels and plasma PK parameters or CSF concentrations of elenbecestat will be explored graphically and any emergent relationship will be explored through population PK/PD modeling. These PK parameters include maximum observed concentration (C_{max}), and $AUC_{(0-24)}$ derived from the population PK model. The PK/PD relationship between plasma PK parameters and CSF concentrations of elenbecestat with other biomarkers may also be explored using similar methods.

Additionally, the relationship between various PK parameters (eg, C_{max}) or CSF concentrations of elenbecestat and CDR-SB at 24 months, and the relationship between various PK exposure parameters or CSF concentrations of elenbecestat and the change from Baseline for 24 months in ADAS-cog14, and the MMSE, will be explored graphically. Any emergent relationships will be explored through population PK/PD modeling. The relationship between exposure to elenbecestat and most frequent AEs will also be explored.

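### Population PK covariates are limited to demographics and CDR-SB exposure-response uses the Month 24 score, so co-dosed donepezil and baseline severity can partly confound that exploratory analysis

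*Protocol*

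**What the plan says.** All references are to the current Version 8.0 text of the Protocol.

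- **Section 7.1, Study 003.** The study looked at the "effects of drug-drug interactions by itraconazole, rifampin, and donepezil on" the drug's pharmacokinetics. Its donepezil result reads: "Donepezil (a moderate CES2 inhibitor) caused a mild increase (by approximately 20%) of the AUC of elenbecestat when coadministered". The rise was absent with a gap of 2 hours or more between the two doses.
- **Appendix 2, Listing 4.** Donepezil is permitted. It may be started, stopped or changed in dose during the study in line with local care. Section 9.4.5 has elenbecestat taken once daily in the morning, and no interval from donepezil is stated.
- **Section 9.7.1.7.1 (same in the synopsis).** The effect of "covariates (ie, demographics) on elenbecestat PK will be evaluated". Population PK is one of the other secondary objectives in Section 8.2.
- **Section 9.7.1.7.2 (same in the synopsis).** Exposure is related to the 24-month score: "concentrations of elenbecestat and CDR-SB at 24 months, and the relationship between". The same sentence goes on to use change from baseline for ADAS-cog14 and MMSE. The relationships are first graphed, and any that emerge go to population PK/PD modelling. No adjustment variables are named. The exposure-efficacy objective is exploratory (Section 8.3).
- **Section 9.7.1.6.1.** The primary model includes "concurrent AD medication use at randomization" as a stratification variable.
- **Table 5, note v.** At the call on the day before PK sampling, "the site staff should document the time that the subject took their study drug that day". No donepezil time is requested.

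**The concern.** The sponsor's own interaction study names a permitted co-medication that shifts exposure, but the stated covariate set leaves it out. The wording is *ie*, which defines the set. Section 9.7.1.7.2 writes *eg* where examples are meant.

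Exposure within the active arm is not randomized. Subjects on donepezil may differ from the rest in baseline severity and rate of decline, and those who take it with the morning dose will tend to have higher AUC. An exposure-response analysis that ignores this can show a relationship where there is none, or hide one. Using the Month 24 score rather than its change adds any baseline difference to that bias. The neighbouring clinical-biomarker ANCOVA in Section 9.7.1.6.2 names baseline score and stratification variables, so the exposure-response text is less complete than the protocol's own practice.

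At stake are the covariate results of the population PK model and the reading of an exploratory exposure-efficacy plot. The trial's main conclusion is not at stake.

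**Working it through.** **Plan figures, Section 9.7.2.** Placebo change 1.46, SD 2.05, 25% reduction, 30% dropout, 90% power, two-sided 0.05.

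- Target effect: 0.25 × 1.46 = 0.365 points.
- n per arm = 2 × (1.960 + 1.282)² × 2.05² / 0.365² = 663. With dropout, 663 / 0.7 gives 948 per arm, or 1896 in total, against 1900 stated. The sample size reproduces and is not in dispute.
- Active-arm completers: 950 × 0.7 = 665.

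**Assumptions (the protocol gives no figures for these).**

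- Donepezil share p: 30% or 50% of the active arm.
- Share of users co-dosing f: all or half.
- Between-subject CV of AUC: 25% or 40%.
- Users' baseline CDR-SB higher by 0.3 or 0.5, and 24-month decline larger by the same amount.
- Baseline SD 1.1.
- No drug effect.

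The AUC ratio of 1.2 for co-dosed users is from Section 7.1.

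**How strongly exposure marks donepezil use.** With b = ln 1.2 = 0.1823, s² = ln(1 + CV²) and c = p × f:

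r = b(c − cp) / √{[b²c(1 − c) + s²] × p(1 − p)}

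- Strongest corner (p = 0.5, f = 1, CV 25%): 0.0456 / √(0.0689 × 0.25) = 0.347, so r² is 12%.
- Weakest corner (p = 0.3, f = 0.5, CV 40%): 0.0191 / √(0.1527 × 0.21) = 0.107, so r² is 1%.
- Over a wider CV range of 20% to 50%, r² runs from about 1% to 17%.

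**Spurious association in the strongest corner.** The user gap g is 0.5 + 0.5 = 1.0 for the raw score and 0.5 for change. The correlation with outcome is r × g × √[p(1 − p)] / SD.

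- Raw score: SD = √(2.05² + 1.1² + 0.25) = 2.38. Correlation 0.347 × 1.0 × 0.5 / 2.38 = 0.073. z = 0.073 × √665 = 1.88. A 5% test rejects about 47% of the time.
- Change: SD = √(2.05² + 0.0625) = 2.07. Correlation 0.042, z = 1.08, rejection about 19%.

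**Whole grid.** Quartile differences are from simulation with 2,000,000 subjects per scenario. Rejection rates use the formula above.

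| Users co-dosing | Outcome | Top minus bottom quartile (points) | Share of 0.365 | Rejection at 5% |
|---|---|---|---|---|
| All | Raw score | 0.15 to 0.45 | 41% to 123% | 10% to 47% |
| All | Change | 0.08 to 0.23 | 21% to 62% | 7% to 19% |
| Half | Raw score | 0.07 to 0.23 | 20% to 62% | 6% to 16% |
| Half | Change | 0.04 to 0.11 | 10% to 31% | 5% to 9% |

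The direction (higher exposure, worse outcome) follows from assuming that users are worse at baseline and decline faster. Change from baseline halves the quartile difference because the baseline and decline gaps are set equal.

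**The case against.** Several points on the other side stand.

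- **Silence on adjustment.** Section 9.7.1.7.2 names no covariates and excludes none, and such detail is often left to an analysis or modelling plan. A reader might infer that the analysis is fixed as unadjusted and that the relationship is confounded. The text supports only a risk.
- **Shorthand.** The CDR-SB endpoint in Section 9.7.1.1.1 is change from baseline, and no raw Month 24 endpoint is defined, so the wording may be loose. But the same sentence writes change for the other two scales, so the text should be corrected.
- **Weak marker.** A reader might infer that exposure stands in for AD-medication use. It does not: donepezil use explains about 1% to 17% of the variance in log AUC under the assumptions. Only co-dosed users are affected, and Listing 4 also includes rivastigmine, galantamine and memantine, so AD-medication use is not the same as donepezil use.
- **No such test is planned.** The protocol specifies graphs and modelling, with neither a quartile contrast nor a 5% test. The rejection rates only gauge size, and the highest one is a single corner of the grid.
- **Data exist.** Section 9.4.7 records all concomitant medication, and Section 9.5.1.4.2 allows exposure to be examined against genetic variants. It would be wrong to say that the trial cannot examine donepezil. What it lacks is dose timing. On PK days study drug is held for the clinic, so donepezil taken at home may fall further from it than usual, which would weaken the donepezil effect in the sampled data.

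**Conclusion.** The point holds in limited form. The covariate set is stated too narrowly for an effect that the protocol itself reports. The CDR-SB exposure-response outcome is also out of line with the primary endpoint and with the other scales in the same sentence. Both are choices on the page, so this is more than detail left for later.

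As written, the exploratory CDR-SB exposure-response can be partly confounded by AD-medication use and carries baseline severity with it. The bias is small to moderate and larger for the raw score than for change. Its size depends on assumed donepezil share, co-dosing, AUC variability and differences between users and non-users. If fewer subjects co-dose, it shrinks.

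A reader might infer that the efficacy conclusion is in doubt. It is not: the primary comparison is randomized, uses change from baseline, and includes concurrent AD medication in the model. The correction is worth making because it is nearly free and population PK is a secondary objective.

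**What to change.** - **Section 9.7.1.7.2 and synopsis:** write change from baseline in CDR-SB at 24 months. State that exposure-response models adjust for baseline score and the stratification variables, including concurrent AD medication.
- **Section 9.7.1.7.1 and synopsis:** replace the demographics-only parenthesis with demographics and concomitant medications, including time-varying donepezil use.
- **Optional:** record the donepezil dose time at the existing day-before call, so that co-dosing can be classified.
- **Separate reconciliation:** Section 7.1 calls donepezil a moderate CES2 inhibitor and says that moderate to strong CES2 inhibitors are not permitted. Listing 1 omits donepezil and Listing 4 permits it. These passages must be reconciled.

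The analysis changes need only wording and a slightly more complex model, using medication data already collected. They need no extra visits, samples or subjects. The optional item adds one time field.
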